### **2.2.8.3. Tumor Assessment**

Tumor response will be assessed by investigators, according to the RECIST 1.1 response criteria.

Complete tumor assessments will be performed approximately every 8 weeks after randomization. Using RECIST 1.1 response criteria, tumor lesions are evaluated separately by target lesions and non-target lesions during each assessment. Then the combined results of target and non-target lesions will provide an overall tumor response for this assessment.

#### **2.2.8.3.1 Response Criteria (RECIST Version 1.1)**

Response evaluation for the target lesions and for the non-target lesions, and new lesions as assessed by the investigator, will be recorded on the CRF and included in the database.

For details on the RECIST Version 1.1 criteria, see Attachment 2 of the PED.

#### **2.2.8.3.2 Evaluation of Overall Response for Each Assessment**

Overall response of the subject at an assessment cycle will be determined based on investigator's assessments on target, non-target and new lesions according to the guidelines below:

Target lesions	Non-target lesions	New lesions	Overall response
CR	CR	No	CR
CR	Non-CR/non-PD	No	PR
CR	Not evaluated	No	PR
PR	Non-PD or not all evaluated	No	PR
SD	Non-PD or not all evaluated	No	SD
Not all evaluated	Non-PD	No	NE
PD	Any	Yes or No	PD
Any	PD	Yes or No	PD
Any	Any	Yes	PD

CR = complete response; PR = partial response; SD = stable disease; PD = progressive disease; NE = Not evaluable.

For subjects with either target or non-target lesions only listed at baseline, the overall response will be evaluated by either the target or non-target lesions only (depending on which is missing), except in the case where a new lesion appears whereby the overall response would then become PD.

Subjects with a clinical deterioration of health status thought by the investigator to be related to disease progression and requiring discontinuation of treatment without objective evidence of disease progression at that time should be reported as “symptomatic deterioration”. Every effort should be made to document the objective progression even after discontinuation of treatment.

### **Date of Progression**

For the analysis based on the investigator’s tumor evaluations, the day of disease progression is determined by using the earliest time point from the following dates: the date of PD as evaluation of response on the CRF; the date of a new lesion on the CRF tumor measurements page.

For the analysis based on all investigator’s data, the day of disease progression is determined by using the earliest time point from the following dates: the date of PD as evaluation of response on the CRF; the date of a new lesion on the CRF tumor measurements page; the death date (if death is caused by PD);, the progression date as documented on the CRF treatment termination page, the progression date as documented on the CRF follow-up visit page.

### **Best Overall response**

The best overall response is the best response recorded from the start of the treatment until disease progression or start of subsequent anticancer therapy. The best overall

YONDELIS®: Statistical Analysis Plan Study ET743-OVC-3006

response will be summarized per treatment group in a frequency table with categories: complete response (CR), partial response (PR), stable disease (SD), progressive disease (PD), not evaluable (NE).

#### **2.2.8.4. Secondary Endpoint: Progression-Free survival**

The analysis of PFS will be based on the data received from the investigator, combined with information from the database on the subject's death and on subsequent therapy for ovarian cancer.

**Progression free survival (PFS)** is defined as the time between the randomization and disease progression or death. Subjects who progressed or died will be considered to have had an event, except if this event occurs after the start of subsequent therapy for ovarian cancer, in which case the subject is censored at the time of last tumor assessment (prior to or on the first day of the first subsequent therapy for ovarian cancer). Subjects who did not progress nor died (lost to follow-up, or still being treated without documented disease progression, or started subsequent therapy for ovarian cancer and still alive) will be censored at the date of the last tumor assessment (prior to or on the first day of the first subsequent therapy for ovarian cancer).

##### **2.2.8.4.1 Handling of Missing Assessments**

Tumor scans are scheduled every 8 weeks for the first 4 assessments and then every 12 weeks. Despite this, assessments are sometimes missing (not performed, not all lesions measured, lost, technically inadequate). If there is a time interval between the last non-PD scan and the date of death or the date of progression, the following algorithm will be applied:

- if a subject has an interval of  $\geq 18$  weeks during the first 4 assessment or  $\geq 26$  weeks thereafter, this is an indication that more than one measurement is missing. Then the PFS is censored at the last disease assessment prior to the interval.
- if a subject has an interval of  $< 18$  weeks prior to the fourth assessment or  $< 26$  weeks after the first 4 assessments, this is an indication that there is only 1 measurement missing, and then the subsequent information (PD date, death date) is used as event.

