## EFFICACY EVALUATIONS/ENDPOINTS

Efficacy will be assessed by a determination of OS, PFS, and ORR. Measurable disease and the response criteria based on measurable disease used in this protocol are defined in the RECIST (Version 1.1) guidelines. Radiological disease assessments (thoraco-abdominal and pelvic computed tomography [CT] scan or magnetic resonance imaging [MRI] measurements and evaluation of extent of disease) will be performed within 30 days before randomization, every 8 weeks (±5 days) after randomization for the first 4 assessments, and then every 12 weeks (±5 days) thereafter. Disease assessments, including assessments for subjects who discontinue treatment for reasons other than disease progression, will be performed until disease progression is radiographically confirmed, the start of subsequent anticancer therapy, withdrawal of subject consent, or the clinical cutoff date.

Assessments must be done consistently in both treatment arms to ensure an unbiased assessment of tumor response and progression. The CA-125 analyses will be performed at a local laboratory. The initial CA-125 evaluation will be performed within 30 days before randomization, approximately every 8 weeks after randomization for the first 4 evaluations, and then approximately every 12 weeks until disease progression is radiographically confirmed, the start of subsequent anticancer therapy, withdrawal of subject consent, or the clinical cutoff date. CA-125 evaluations should coincide (±5 days) with the scheduled tumor assessments. Survival follow-up will continue for all enrolled subjects until at least 514 deaths are observed or until the clinical cutoff date.

As of Amendment 6, follow-up data will no longer be collected.

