### **9.1.3.4. Tumor Assessment**

Measurable disease and the response criteria used in this protocol are defined in the RECIST guidelines (Version 1.1) ([Attachment 2](#)) and will be based on radiologic assessment only.

Every effort should be made to ensure that the same radiographic method of disease assessment (computed tomography [CT] scans or magnetic resonance imaging [MRI]) be used throughout the study. Disease assessment procedures to evaluate objective response must be consistent with RECIST (Version 1.1) guidelines for radiologic assessment, as presented in [Attachment 2](#), RECIST Guidelines. The disease assessments should include, at a minimum, imaging of the chest (with lung views) abdomen, and pelvis. All disease assessments, including CA-125 measurements, will be performed within 30 days before randomization, every 8 weeks ( $\pm 5$  days) from the date of randomization for the first 4 assessments, and then every 12 weeks ( $\pm 5$  days) until disease progression is radiographically confirmed, the start of subsequent anticancer therapy, withdrawal of subject consent, or the clinical cutoff date. Disease assessments should be performed at the treatment termination visit and according to schedule thereafter if disease progression or follow-up therapy has not been documented. Every effort should be made to ensure that these assessments are done on the required date, although a window of  $\pm 5$  days will be accommodated.

In case of clinical progression, radiologic assessments should proceed according to the original Time and Events Schedule or as clinically indicated. The date of progression will be defined as the date of the first imaging study that documents progression.

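### The PFS missing-scan rule is not defined for gaps across the 8-to-12-week switch or from the baseline scan, and its more natural reading at the switch censors a progression after a single missed scan

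*SAP*

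**What the plan says.** SAP 2.2.8.4.1 states the schedule: "Tumor scans are scheduled every 8 weeks for the first 4 assessments and then every 12 weeks". Protocol Synopsis, Efficacy Evaluations/Endpoints, adds the windows: "every 8 weeks (±5 days) after randomization for the first 4 assessments, and then every 12 weeks (±5 days) thereafter".

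The gap rule measures from the last non-PD scan to progression or death. The first bullet covers an interval of at least 18 "weeks during the first 4 assessment or" at least 26 weeks after that, and gives its reason: "this is an indication that more than one measurement is missing". PFS is then censored at the last assessment before the gap. The second bullet covers an interval of under 18 "weeks prior to the fourth assessment or" under 26 weeks after the first four; this is taken as one missing scan and the event is kept.

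SAP 2.2.8.4 measures PFS from randomisation. Subjects without progression or death "will be censored at the date of the last tumor assessment" before any subsequent ovarian cancer therapy. On baseline timing, Protocol 9.1.3.4 says: "All disease assessments, including CA-125 measurements, will be performed within 30 days before randomization".

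The SAP does not say:

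- which limit applies to a gap that begins before the fourth assessment and ends after it;
- whether the fourth assessment means the fourth scheduled or the fourth performed;
- whether the baseline scan is a non-PD scan;
- what date to use when there is no post-baseline scan.

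**The concern.** The rule uses the length of a gap as a stand-in for the number of missed scans. That works while the spacing is constant. It can fail where the spacing changes, and where the gap starts at a scan taken before the PFS clock starts. At those two places one missed scan can produce a gap above 18 weeks, so a progression that the rule means to keep would be censored.

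The two bullets also describe the early period differently: one speaks of the span of the first four assessments, the other of the time before the fourth. Two programmers working from the same text could classify the same subject differently. The classification feeds the PFS log-rank test, hazard ratio, medians and six-month and one-year rates that SAP 2.2.8.4.2 still plans.

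**Working it through.** **Inputs.** Scans at weeks 8, 16, 24, 32, then 44, 56, 68 (SAP 2.2.8.4.1). Window ±5 days per scan, so a gap between two scans can move by ±10 days, which is ±1.43 weeks. Baseline scan up to 30 days (4.29 weeks) before randomisation.

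**Step 1: the plan's limits within each phase.**

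- 8-week phase: one missed scan gives 16 weeks, at most 16 + 1.43 = 17.43, below 18. Two missed give 24, at least 24 − 1.43 = 22.57, above 18.
- 12-week phase: one missed gives 24, at most 25.43, below 26. Two missed give 36, at least 34.57, above 26.

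For scan-detected progression, both limits reproduce as sensible within their own phase.

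**Step 2: around the switch.**

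| Last non-PD scan to PD (weeks) | Scans missed | Gap in weeks (range) | At least 18? | At least 26? |
|---|---|---|---|---|
| 24 to 44 | 1 | 20 (18.57-21.43) | always | never |
| 16 to 44 | 2 | 28 (26.57-29.43) | always | always |
| 24 to 56 | 2 | 32 (30.57-33.43) | always | always |
| 32 to 56 | 1 | 24 (22.57-25.43) | always | never |

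The last row starts at the fourth assessment, so the 26-week limit applies and the event is kept. The first row is the problem. At 18 weeks it is always censored at week 24; at 26 weeks it is always an event. A death 18 to 20 weeks after the week-24 scan, with only week 32 missed, is affected in the same way.

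The 18-week limit is the more natural reading of the first row. The interval begins before the fourth assessment. If performed scans are counted, week 44 is itself the fourth.

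**Step 3: from the baseline scan.** Take a baseline scan d days before randomisation, week 8 missed and progression at week 16. The gap is 16 + d/7 weeks.

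- d = 14: 18.0 weeks, so the limit is reached.
- d = 30: 20.29 weeks.
- If the week-16 scan is 5 days late, d = 9 is enough (16 + 9/7 + 5/7 = 18.0).

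Censoring at the last assessment before the gap then falls before randomisation. Measured from randomisation instead, the gap is at most 16 + 5/7 = 16.71 weeks and the event is kept.

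**Step 4: size (illustration only).** Assume exponential PFS with the medians of 5.8 and 7.3 months from the earlier second-line study (Protocol 1.4), or 25.2 and 31.7 weeks. Assume each scan is missed independently with probability p, no deaths, and every subject eventually progressing. Write S(t) for the probability of being progression-free at week t.

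- Switch: [S(24) − S(44)] × p(1 − p)². The bracket is 0.219 for the shorter median and 0.210 for the longer. At p = 5% this gives 0.99% and 0.95%; at p = 10%, 1.77% and 1.70%.
- Baseline: [1 − S(16)] × p(1 − p) × 16/30, with scan dates uniform over the 30 days before randomisation. The bracket is 0.356 and 0.295. At p = 5% this gives 0.90% and 0.75%; at p = 10%, 1.71% and 1.42%.
- Both together: 1.7-1.9% at p = 5% and 3.1-3.5% at p = 10%.

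**The case against.** **The text can be read the other way at the switch.** A gap ending at the fifth assessment is not plainly within the first four, and the later-period wording could give it the 26-week limit. If neither bullet covers it, the general definition in SAP 2.2.8.4 makes the progression an event. The rule's stated purpose also favours keeping it. This stands: a reader might infer that real events will certainly be censored, but the documents support only that the rule is undefined here and that its more natural reading miscensors.

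**Baseline may be outside the rule.** Non-PD is a response status judged against baseline, and the first four assessments are those after randomisation. On that view the rule never starts from the baseline scan. This stands too, so the baseline result is conditional on the reading and on a scan about 14 or more days old.

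**Negative times.** A reader might infer that every subject without a post-baseline scan gets a negative PFS time, and that software then drops her from the All Randomized set. The documents do not support this. Subjects who die are events under SAP 2.2.8.4 unless subsequent therapy came first, a baseline scan on the day of randomisation gives zero, and nothing is said about software. What remains is that the wording gives event-free subjects with only a baseline scan a date on or before randomisation, with no fallback.

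**The illustration is simplified.** It leaves out termination-visit scans (Protocol 9.1.4) and unscheduled scans (Protocol 9.1.3.4), either of which can break a gap, and also deaths and the 18 January 2018 cut-off. Scan timing is the same in both arms, so no distortion of the hazard ratio is shown.

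**Importance.** PFS is secondary, and SAP 2.2.8.1.1 drops the hierarchical testing. That limits the weight of the point. It does not remove it, because the PFS estimates are still to be produced.

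**Conclusion.** The point holds as a specification fault at two boundaries and one missing date. The limits are sound for scan-to-scan gaps within each phase. At the switch, the more natural reading censors at week 24 a subject with one missed scan and progression at week 44. From baseline, the same can happen if that scan counts as non-PD and is old enough. For event-free subjects with no post-baseline scan, the censoring date as worded does not fall after time zero.

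The size is about 1-2% of PFS events from the switch alone, and about 2-3.5% if the baseline reading also applies. Both figures rest on assumed miss rates of 5-10%, which the documents do not give, on exponential PFS with the earlier study's medians, and on the simplifications named above. The OS analysis and the futility decision are untouched. The rule should be corrected before PFS is analysed, but it does not threaten the trial's main conclusion.

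**What to change.** Replace the week limits in SAP 2.2.8.4.1 with a count:

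1. Censor at the last adequate assessment only when two or more consecutive scheduled scans are missed before the progression or death. State that scheduled scans are counted, and how a scan outside its ±5-day window is treated.
2. When there is no post-baseline scan, start the first gap at randomisation.
3. Censor a subject with no post-baseline scan and no event at the randomisation date.

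A separate 22-week limit for gaps spanning the fourth scan may look like a simpler route, but it is not equivalent. With the last scan at week 16, weeks 24 and 32 both missed and death at week 36, the gap is 20 weeks. The 22-week limit keeps the event although two scans were missed. Unscheduled progression scans cause the same mismatch.

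The count also changes a few cases within a phase. With the last scan at week 8, weeks 16 and 24 missed and death at week 25, the gap is 17 weeks: the present rule keeps this event and the count would censor it. That agrees with the stated aim but should be a deliberate choice.

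SAP 2.1.1, 2.2.8.3 and 2.2.8.6.1 still describe 8-weekly assessments only and should be reconciled with 2.2.8.4.1. The cost is a few lines of SAP text and programming, with no new data.

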##### **2.2.8.4.2 Analysis Methods**

PFS will be compared between treatment arms using an unstratified two-sided log-rank test. The Kaplan-Meier method will be used to estimate the distribution functions of PFS for each treatment arm. The number of events, subjects censored, the estimate of medians and 95% confidence interval for the medians will be presented. The plots of PFS using the Kaplan-Meier method will be presented. Six-month and one-year progression-free rates will be calculated using the Kaplan-Meier method. The

YONDELIS®: Statistical Analysis Plan Study ET743-OVC-3006

unstratified Cox proportional hazards model will be used to obtain the HR and its 95% CI.

#### **2.2.8.5. Other Secondary Efficacy Analyses**

##### **2.2.8.5.1 Definition of Other Secondary Efficacy Variables**

###### **Objective Response**

*Objective response* is defined as having "CR" or "PR" as best overall response based on reconciled tumor assessment. Detail tumor response evaluation is described previously. The *objective response rate* is calculated as the number of objective responders divided by the number of subjects.

The response rate variable will be evaluated using the Chi-square statistic (unstratified).

##### **2.2.8.5.2 Analysis Methods**

The best overall response will be summarized per treatment arm in a frequency table with categories: complete response (CR), partial response (PR), stable disease (SD), progressive disease (PD), not evaluable (NE).

Subjects' overall response per cycle assessment will be determined and will be presented in a listing.

The response rate variable will be evaluated using the Chi-square statistic (unstratified).

#### **2.2.8.6. Supportive Analyses**

##### **2.2.8.6.1 Symmetry of Tumor Assessment Schedules**

Tumor assessments were to be performed every 8 weeks. Timing of assessments in both treatment groups will be presented side by side with boxplots.

##### **2.2.8.7. ECOG**

The ECOG value at the end of treatment visit will be tabulated (not cross-tabulated against the baseline value). The listing will contain both ECOG values.

##### **2.2.8.8. Patient Reported Outcomes**

The following preplanned patient reported outcome analysis will not be performed due to lack of efficacy per the futility analysis.

The Patient Reported Outcomes will be measured by the OV28 and the EQ-5D questionnaires. Patients will be requested to fill these out at baseline, at the end of every cycle, at the treatment termination visit, and every 8 weeks till start of subsequent treatment. The analyses of these data will be performed on summary scores as well as subscales, and individual symptoms.

YONDELIS®: Statistical Analysis Plan Study ET743-OVC-3006

Change from baseline at each time point and treatment termination will be analysed for selected scales of the OV28 items. In particular, Abdominal/Gastrointestinal Symptoms scales of OV28 will be tested based on the grouping criteria as specified in Greimel et al. Mean score changes from baseline at each time point and treatment termination will be compared between the treatment arms using T-test. The changes will also be analyzed using model for longitudinal data, taking the potential missing data and dropout into account.

#### **2.2.8.9. Subsequent treatment**

Frequency tabulation will be given, indicating how many subjects in each arm started subsequent therapy for ovarian cancer.

The accompanying listing will contain details on the type of subsequent therapy for ovarian cancer as well as the start date.

#### **2.2.9. Safety**

##### **2.2.9.1. Adverse Events**

Treatment emergent adverse events will be summarized by disease group and overall. A treatment-emergent adverse event is defined as any AE occurring or worsening on or after the first treatment of DOXIL/Trabectedin, and within 30 days after the last dose. For imputation rules for incomplete dates, see Attachment 4.1.

Adverse events are documented on the CRF together with their severity, according to the NCI CTC version 4.0, also referred to as NCI toxicity grading. For the categorization of the adverse events, the MedDRA dictionary will be used. Adverse events are considered drug related when the relation to trial medication is considered to be possible, probable, or very likely, according to the investigator's opinion.

Summary of overall adverse events will be done by body system and preferred term, by severity (worst toxicity grade), by relationship to the study drugs (trabectedin or DOXIL), and by AE outcome. Tables will be sorted by body system/preferred term and by the highest incidence. In the AE database, "neoplasm malignant aggravated", and "condition aggravated" are created terms to match the Global Medical Safety (GMS) death reporting database (in case of death due to disease progression). These will not be included in the AE summaries.

A listing will be prepared on all adverse events. If data is available, a listing for delayed adverse events (defined as new onset of AE occurring 30 days after last dose as judged by investigator to be related to trial medication) will be presented.

YONDELIS®: Statistical Analysis Plan Study ET743-OVC-3006

First occurrence of grade 3 and 4 adverse events will be reported by cycle. The drug related grade 3 and 4 adverse events would be summarized.

A frequency table will be made for the AEs leading to cycle delay, dose reduction, skipped dose, or withdrawal of study medication. Adverse events leading to permanent stop and AE with outcome death will also be presented by drug relatedness.

For all serious adverse events (SAEs), the investigator has to send an SAE form to the Janssen R&D GMS. The AEs that are indicated on the CRF as serious are used for the summary tables. A summary table by any grade SAEs will be presented. A similar table will be presented for the drug-related SAEs.

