### Treatment Allocation

#### *Procedures for Stratification and Randomization*

Prior to randomization, inclusion criteria #4 through #8 must be reviewed by sponsor's medical monitor (Section 4.1, Inclusion Criteria). Following sponsor review, subjects will be stratified by the time from the last dose of first-line platinum therapy to disease progression (6 months to 12 months vs >12 months to 24 months vs >24 months), ECOG performance status grade (0 vs 1), BRCA 1/2 status (mutation vs no mutation), and prior DOXIL therapy (no vs yes). Central randomization will be implemented in this study. Randomization of subjects should occur as close in time as possible before administration of the first dose of study drug(s) and must occur within 7 days of the subject receiving the first dose of study treatment. This maximum 7-day window is given to allow time for provision of central venous access for those subjects assigned to Treatment Arm A (Section 6, Dosage and Administration). Subjects will be randomly assigned, in a 1:1 ratio, to 1 of 2 treatment groups based on a computer-generated randomization schedule prepared before the study by or under the supervision of the sponsor. The interactive voice response system (IVRS) and/or interactive web response system (IWRS)

will assign a unique treatment code, which will dictate the treatment assignment and matching study drug kit for the subject. The requestor must use his or her own user identification and personal identification number when contacting the IVRS/IWRS, and will then give the relevant subject details to uniquely identify the subject.

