#### **Adverse Events**

The verbatim terms used in the CRF by investigators to identify adverse events will be coded using the Medical Dictionary for Regulatory Activities (MedDRA) and will be graded according to the NCI-CTCAE, Version 4.0. All reported adverse events with onset during the treatment phase (ie, those events that occur or worsen on or after the first dose of study drug up through 30 days after the last dose of study drug) will be included in the analysis. Adverse events will be summarized by MedDRA system organ class and preferred term. For each adverse event, the percentage of subjects who experience at least 1 occurrence of the given event will be summarized overall and by treatment group. Serious adverse events and deaths will be listed. All adverse events resulting in discontinuation of study treatment, dose modification, the interruption of dosing, or a delay in treatment with the study drug will be listed and summarized by preferred term.

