**12.3. Procedures****12.3.1. All Adverse Events**

All adverse events and special reporting situations, whether serious or non-serious, will be reported from the time a signed and dated ICF is obtained until 30 days after the administration of the last dose of study drug or until the scheduled treatment termination visit on or prior to 18 January 2018. Any drug-related Grade 3 or 4 toxicities will be followed by the investigator until Grade 2 or less, for a maximum of 6 months after the last dose of study drug, or until the scheduled treatment termination visit on or prior to 18 January 2018, whichever occurs first. Grade 2 to 4 liver or cardiac toxicities will be monitored until Grade 1 or less, for a maximum of 6 months after the last dose of study drug, or until the scheduled treatment termination visit on or prior to 18 January 2018, whichever occurs first.

Serious adverse events, including those spontaneously reported to the investigator within 30 days after the last dose of study drug, must be reported using the Serious Adverse Event Form. The sponsor will evaluate any safety information that is spontaneously reported by an investigator beyond the time frame specified in the protocol. All events that meet the definition of a serious adverse event will be reported as serious adverse events, regardless of whether they are protocol-specific assessments.

All adverse events, regardless of seriousness, severity, or presumed relationship to study drug, must be recorded using medical terminology in the source document and the CRF. Whenever possible, diagnoses should be given when signs and symptoms are due to a common etiology (eg, cough, runny nose, sneezing, sore throat, and head congestion should be reported as "upper respiratory infection"). Investigators must record in the CRF their opinion concerning the

relationship of the adverse event to study therapy. All measures required for adverse event management must be recorded in the source document and reported according to sponsor instructions.

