### **2.1.3.2. Safety Analysis Set**

The safety analysis is based on the “All Treated Subject” analysis set, where the grouping into the different arms is based on the true treatment received during the first cycle.

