#### **2.2.10. Safety Narratives**

Safety narratives will be written for the following 3 groups of subjects:

1. Deaths for reasons other than disease progression that occurred within 30 days of the last dose of study medication;
2. Treatment-emergent serious adverse events;
3. Treatment-emergent adverse events that led to discontinuation of study medication

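### Complications of placing the central line that only Arm A requires, if they start before first dose, fall outside the treatment-emergent tables and the safety narratives

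*SAP*

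**What the plan says.** **The procedure.** Protocol Section 5 (Blinding) gives the catheter requirement, confined to the combination arm, as the reason the trial is open label. On the gap between randomisation and first dose, the same section says: "This maximum 7-day window is given to allow time for provision of central venous access for those subjects assigned to Treatment Arm A". Section 6 repeats that purpose. It also lets Arm B receive DOXIL by either a central or a peripheral line, and Section 16.1 describes the comparator as generally given peripherally.

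**Collection.** Under Protocol Section 12.3.1, adverse events "will be reported from the time a signed and dated ICF is obtained until 30 days after the administration of the last dose". An event in the gap is therefore recorded.

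**Tabulation.** SAP Section 2.2.9.1 defines a treatment-emergent event as "any AE occurring or worsening on or after the first treatment of DOXIL/Trabectedin", with the window closing 30 days after the last dose. Protocol Section 11.7 sets the same start for the events that enter the analysis: "those events that occur or worsen on or after the first dose of study drug up through 30 days after the last dose". SAP Section 2.1.3.2 adds: "The safety analysis is based on the “All Treated Subject” analysis set". SAP Section 2.1.3 limits that set to randomised subjects given at least one dose of either drug.

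**Narratives.** SAP Section 2.2.10 names three groups: non-progression deaths up to 30 days after the last dose, "Treatment-emergent serious adverse events", and treatment-emergent events that led to stopping study drug.

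**Other outputs.** SAP Section 2.2.9.1 also plans a listing of every adverse event. It builds the serious-event tables from events flagged serious on the CRF and does not repeat the treatment-emergent limit there. SAP Section 2.2.4 gives disposition by randomised arm (treated or not treated), a listing of untreated subjects, and termination reasons over all randomised subjects, with adverse event and death among the categories.

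**The concern.** Placing the line follows from being allocated to Arm A and happens after randomisation, so its complications are harms of the assigned regimen. The safety clock starts later, at the first infusion. Arm B subjects may have a central line but do not need one, so the part left uncounted lies mainly in one arm and makes the experimental regimen look safer than it is.

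At stake is the comparison behind a secondary objective, the safety of the two regimens. Higher toxicity in Arm A was also one of the two reasons the monitoring committee gave for recommending that the study stop.

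**Working it through.** The plan states no figure on this point, so there is none to reproduce. The check sets three windows side by side and follows each kind of event through the planned outputs.

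**Windows**

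- Collection: consent to last dose + 30 days (Protocol 12.3.1).
- Line placement: randomisation to first dose, at most 7 days (Protocol 5 and 6).
- Tabulation: first dose to last dose + 30 days (Protocol 11.7, SAP 2.2.9.1).

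Placement lies inside collection and, where a new line is put in during this gap, before tabulation begins.

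**Where a line complication would appear**

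| Event | Treatment-emergent tables | Serious-event tables | Narrative | Elsewhere |
|---|---|---|---|---|
| Starts before first dose, no later worsening, not serious, subject dosed | No | Not applicable | No | All-event listing |
| Same, but serious | No | Unclear: SAP 2.2.9.1 sets no limit in that sentence, Protocol 11.7 would exclude it | No | All-event listing |
| Prevents any dose | No, outside the safety set | No if serious, where the safety set is applied | No, there is no last dose and nothing is treatment-emergent | All-event and not-treated listings; not-treated count by arm; possibly a termination reason that does not name the event |
| Starts or worsens at or after first dose | Yes | Yes if serious | Yes if serious or if it led to stopping | Listing |
| Start day unknown, same month as first dose | Yes, SAP 4.1 moves the start to first dose | Yes if serious | As in the row above | Listing |

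The first and last rows show an inconsistency. The same non-serious event is excluded when its start is fully dated and counted when the day is missing.

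A fatal complication in a subject never dosed would still be a death in the overall survival analysis, which uses all randomised subjects. The death tables in SAP Section 2.2.9.4 are anchored to treatment.

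**Size**

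Affected subjects = N × s × r, where:

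- N = 335, the planned Arm A size (Protocol 3.1, SAP 1.2);
- s = share of Arm A needing a new line, assumed 25% to 100%;
- r = proportion of those with a complication before first dose, assumed 0.5% to 5%.

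Neither s nor r is in the documents.

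| s | r | N × s × r | % of Arm A |
|---|---|---|---|
| 25% | 0.5% | 335 × 0.25 × 0.005 = 0.4 | 0.1% |
| 50% | 1% | 335 × 0.50 × 0.01 = 1.7 | 0.5% |
| 100% | 3% | 335 × 1.00 × 0.03 = 10.0 | 3.0% |
| 100% | 5% | 335 × 1.00 × 0.05 = 16.8 | 5.0% |

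Randomisation ended early and the actual Arm A size is not given, so the counts may be too high. The percentages do not depend on N.

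**The case against.** The case for leaving the plan alone has real weight. Counting from first dose in treated subjects is a defined convention on which protocol and SAP agree. The gap is narrow: at most 7 days of onset without later worsening, plus subjects never dosed. Everything after first dose is counted. The events are not hidden, because they are listed, and a subject who is not dosed shows up in disposition by arm. The trial stopped on a survival hazard ratio of 0.962 against a futility threshold of 0.93, together with higher Arm A toxicity. Extra Arm A events would only reinforce that decision.

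Most of this stands, and it rules out two stronger readings that a reader might infer.

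- **That these events appear in no adverse-event table at all.** The SAP sentence on serious events does not restate the treatment-emergent limit, so a pre-dose serious event in a subject later dosed might be tabulated. The documents leave this open.
- **That Arm A toxicity is in fact understated, with nothing comparable in Arm B.** The documents give no complication rate, no share of subjects who already had a line, and no count of central lines in Arm B, where they are permitted. They support a direction of risk, not a measured bias.

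The objection does not remove the gap. A listing gives no incidence by arm, a termination reason does not name the event, and no narrative category reaches a serious complication confined to the pre-dose period. The usual convention also assumes that nothing done because of allocation happens before the first dose, whereas here the protocol sets time aside for such a procedure.

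**Conclusion.** The point holds in limited form. Followed as written, the plan leaves placement complications that start before first dose and do not worsen out of the treatment-emergent tables and the narratives. It also drops subjects never dosed because of them from the safety set. Whether serious ones reach the serious-event tables is unresolved between Protocol Section 11.7 and SAP Section 2.2.9.1. Because only Arm A must have the catheter, any understatement falls mainly on that arm.

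The size is unknown. The illustrative range of 0.1% to 5.0% of Arm A rests wholly on the assumed share and rate. Nothing suggests that the stopping decision or any efficacy result would change. What improves is the completeness of the safety comparison, and since the data are already collected, the correction is worth making.

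**What to change.** 1. Add to SAP Section 2.2.9.1 a supplementary table by randomised arm, in All Randomized Subjects, of adverse events and serious adverse events with onset from randomisation to before first dose. Identify catheter-related terms, and add a row that pools those terms with the treatment-emergent period.
2. State in the same section whether the serious-event tables are limited to treatment-emergent events, and bring it into line with Protocol Section 11.7.
3. Extend SAP Section 2.2.10 to narrate serious adverse events and non-progression deaths from randomisation onward.
4. State how incomplete start dates are handled in the new table. The present rule sets an event in a month before the month of first dose to day 1 of its month, which could fall before randomisation.

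The cost is one extra table, a few narratives and slightly less favourable reported toxicity for Arm A. No new data collection is needed, and the efficacy analyses are untouched.
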